8.1.2 TFD/TPI

Details of TFD/TPI treatment administration on Days 1 to 5 and Days 8 to 12 of each cycle of study treatment will be listed. The listing will include prescribed total daily dose, date of TFD/TPI administration, time of morning dose, number of 15mg and 20mg tablets taken in the morning, time of evening dose, number of 15mg and 20mg tablets taken in the evening and total daily dose administered. A separate listing of compliance to TFD/TPI treatment will be presented. This will include, overall and in each cycle, the total dosage administered, the prescribed total daily dose, expected number of dosing days, expected dosage and the percentage compliance.

Summary statistics will be presented for the total dose of TFD/TPI received across all cycles and for the total duration of exposure to TFD/TPI.

Total duration of exposure will be calculated in days as follows:

$$\text{Total duration of Exposure} = (\text{Date of Last Dose of TFD/TPI} - \text{Date of First Dose of TFD/TPI}) + 30$$

Summary statistics will be presented for overall percentage compliance, and by cycle, together with a categorical summary of the number and percentage of participants who were <80%, 80-90%, and >90% compliant with respect to taking the prescribed TFD/TPI dose.

8.2 Adverse events

The primary safety endpoints for Part B of this study are the incidence and severity of TEAEs (including SAEs) from the first dose of UCB6114 treatment on Day 1 of Cycle 1 until the end of the SFU Period (up to 30 days following the last dose of UCB6114 treatment), and the incidence of DLTs from the first dose of UCB6114 on Day 1 of Cycle 1 until the end of the 28-day DLT Observation Period (Day 28 of Cycle 1).

All AEs in Part B of the study will be coded using MedDRA® and classified as pre-treatment and treatment-emergent relative to the first dose of UCB6114 treatment. Adverse events with a start date prior to the first infusion of UCB6114 will be defined as pre-treatment AEs. A TEAE is defined as any AE with a start date on or after the first dose of UCB6114 up until the last dose of UCB6114 + 30 days. A pre-treatment AE which increases in severity on or after the first dose of UCB6114 will also be counted as a TEAE. Note that in this case, the pre-existing AE will have a stop date and an outcome of ‘worsened’ and a new AE (with the same verbatim) will be entered with the same start date and the increased severity recorded on the eCRF. Any AE (including SAEs) with an onset date later than the last dose of UCB6114 + 30 days will not be considered as treatment-emergent and therefore will not be included in the tabulations of TEAEs. These AEs will be considered as post-study AEs and will be listed only. Where onset dates are missing or partially missing, AEs will be assumed to be treatment-emergent, unless there is clear evidence to suggest that the AE started prior to the first dose of UCB6114 and it has not increased in severity. Missing or partially missing dates for AEs will be handled as described in [Section 4.2.3](#) All AEs for a participant will be recorded in the eCRF from the time of informed consent until completion or early discontinuation of Part B of this study. Serious adverse events are to be reported up to 30 days after the Final Visit (i.e. up to 150 days after the last dose of study treatment).

Adverse events will be assigned an NCI CTCAE severity grade (Grade 1/Grade 2/Grade 3/Grade 4/Grade 5), where possible. If a CTCAE toxicity grading is not possible, then the intensity of the AE (mild/moderate/severe) will be recorded on the eCRF. If the AE is not gradable, is serious, and is considered as life threatening, then the intensity for this AE will be missing and one of the reasons for seriousness will be recorded as life threatening. Adverse events will also be categorized according to their relationship to UCB6114 and/or TPD/TPI treatment (related/not related), and whether the event is a DLT, as judged by the investigator. A DLT is defined as a TEAE at least possibly related to UCB6114 that occurs during Cycle 1 and fulfills any of the criteria listed in Section 4.1.1.4 of the protocol. The investigator is expected to record whether an AE is a DLT on the eCRF.

An overview of the number and percentage of participants who experience TEAEs will be presented. This summary will include the number and percentage of participants with any TEAEs, serious TEAEs, related TEAEs (related to UCB6114 only and related to UCB6114 and/or TFD/TPI), discontinuations from study treatment (UCB6114 and TFD/TPI and TFD/TPI only) due to TEAE(s), discontinuations from the study due to TEAE(s), CTCAE Grade ≥ 3 TEAEs, CTCAE Grade ≥ 3 TEAEs related to UCB6114 only, CTCAE Grade ≥ 3 TEAEs related to UCB6114 and/or TFD/TPI, DLTs, AEs leading to death and TEAEs leading to death; event counts will also be included against each of these categories. The overview of TEAEs will be presented by Gastric/GEJ-Cancer and CRC tumor type depending on the number of participants with specific tumor types.

In addition, the following summaries will be presented by SOC, high level term (HLT) and PT, and where indicated also by Gastric/GEJ-Cancer and CRC tumor type depending on the number of participants with specific tumor types:

- Incidence of TEAEs (overall and by tumor type);
- Incidence of serious TEAEs (overall and by tumor type);
- Incidence of non-serious TEAEs (overall and by tumor type);
- Incidence of TEAEs leading to a temporary interruption of UCB6114 infusion and/or dose reduction (overall and by tumor type);
- Incidence of TEAEs leading to a temporary interruption and/or reduction in dose of TFD/TPI (overall and by tumor type);
- Incidence of TEAEs leading to discontinuation of UCB6114 and TFD/TPI (overall and by tumor type);
- Incidence of TEAEs leading to discontinuation of TFD/TPI only (overall and by tumor type);
- Incidence of TEAEs leading to discontinuation of study (overall and by tumor type);
- Incidence of DLTs (separately for during the 28-day DLT Observation Period and after the 28-day DLT Observation Period) (overall and by tumor type);
- Incidence of adverse events of special interest (AESIs) (Hy's Law – see [Section 8.2.1](#) below) (overall and by tumor type);

- Incidence of UCB6114 infusion-related reactions (defined any TEAE with a PT from both a narrow and broad scope search of category A terms of the ‘Hypersensitivity’ Standardized MedDRA® Query (SMQ) – see [Section 8.2.2](#)) (overall and by tumor type);
- Incidence of TEAEs by maximum CTCAE severity grade (overall and by tumor type);
- Incidence of TEAEs related to UCB6114 only by maximum CTCAE severity grade (overall and by tumor type);
- Incidence of TEAEs related to UCB6114 and/or TFD/TPI by maximum CTCAE severity grade (overall and by tumor type);
- Incidence of TEAEs by maximum relationship to UCB6114 only (overall and by tumor type);
- Incidence of TEAEs by maximum relationship to UCB6114 and/or TFD/TPI (overall and by tumor type);
- Incidence of TEAEs by relationship to UCB6114 only;
- Incidence of TEAEs by relationship to UCB6114 and/or TFD/TPI;
- Incidence of serious TEAEs by relationship to UCB6114 only;
- Incidence of serious TEAEs by relationship to UCB6114 and/or TFD/TPI;
- Incidence of non-serious TEAEs by relationship to UCB6114 only;
- Incidence of non-serious TEAEs by relationship to UCB6114 and/or TFD/TPI;
- Incidence of fatal TEAEs by relationship to UCB6114 only;
- Incidence of fatal TEAEs by relationship to UCB6114 and/or TFD/TPI;
- Incidence and event rate of TEAEs by treatment-emergent ADA positivity.

The following summary will be presented by SOC and PT for EudraCT reporting:

- Incidence of non-serious TEAEs above the threshold of 5% of participants in any treatment group.

The above summaries of TEAEs will be ordered alphabetically by SOC, alphabetically by HLT within SOC and decreasing incidence of PT events within SOC /HLT in all study participants. For tables including only the number and percentage of participants, summaries will be ordered alphabetically by SOC, alphabetically by HLT within SOC and decreasing incidence of participants with each PT within SOC /HLT in all study participants.

The incidence of TEAEs by maximum CTCAE severity grade will be presented by CTCAE term. CTCAE term will be obtained from the NCI CTCAE Version 5.0 via a mapping of MedDRA® lower level terms. This summary will be ordered by decreasing incidence of participants with each CTCAE term in all study participants.

Summary tables will contain frequency counts and percentages, and the number of events, where applicable. A study participant who experiences the same event multiple times will be counted only once in the frequency counts for the PT, but all events will be included.

In the summaries of TEAEs by relationship, participants will be counted in “Not related” and “Related” categories (or “Missing” in the case where an event has a missing relationship). A study participant who experiences the same event multiple times will be included in the most related category for the summaries by maximum relationship.

In the overview summary of TEAEs, participants will be counted as having at least one TEAE with CTCAE severity grade ≥ 3 , and in the summary of TEAEs by maximum CTCAE severity grade, participants will be counted as having at least one TEAE in the following categories: ‘Grade 1’, ‘Grade 2’, ‘Grade 3’, ‘Grade 4’, ‘Grade 5’, ‘Grade 3 or 4’ and ‘Grade ≥ 3 ’. Events for which no CTCAE severity grade is recorded by the investigator but an intensity is recorded instead, the intensity of this event will be assigned to a CTCAE severity grade for the purpose of these summaries, i.e. ‘Mild’ will be included as ‘Grade 1’, ‘Moderate’ will be included as ‘Grade 2’, ‘Severe’ will be included as ‘Grade 3’, ‘Life Threatening’ will be included as ‘Grade 4’ and, if the participant dies due to the event, it will be included as ‘Grade 5’. The determination of whether the event is life threatening or results in death will be based on the reason for seriousness recorded as life-threatening or death on the eCRF, or on the event having a fatal outcome. Otherwise, if both the CTCAE severity grade and intensity is missing then the CTCAE severity grade in these summaries will be missing. A study participant who experiences the same event multiple times will be included in the highest severity grade category in the summary of TEAEs by maximum CTCAE severity grade.

A glossary of all AEs will be presented including the MedDRA® SOC, HLT, PT, reported term and low level term (LLT).

A listing of all AEs will be presented by study participant for the ES. The listing will include the onset date and stop date of the event (including relative days) and also the onset times and stop times of events where available. Period of onset of AEs will also be presented on this listing.

Period of onset of AEs will be defined as follows for the purpose of the listing:

- If the AE has an onset date prior to the date of the Screening visit, then Period=Pre-study;
- If the AE has an onset date on or after the date of the Screening visit and has an onset date and time prior to the start time of UCB6114 infusion on Day 1 of Cycle 1 then Period=Screening;
- If the AE has an onset date and time on or after the start time of UCB6114 infusion on Day 1 of Cycle 1 and up to the date and time of the start of Cycle 2 (i.e. prior to the start time of the UCB6114 infusion on Day 1 of Cycle 2) then Period=Cycle 1;
- If the AE has an onset date and time on or after the start time of UCB6114 infusion on Day 1 of Cycle 2 and up to the date and time of the start of Cycle 3 (i.e. prior to the start time of the UCB6114 infusion on Day 1 of Cycle 3) then Period=Cycle 2;
- Same as above for subsequent cycles (Cycle 3 etc.);
- If the AE has an onset date after the last dose of UCB6114 up to and including 30 days after the last dose of UCB6114, then Period=SFU;
- If the event has an onset date after the 30-day period following the last dose of UCB6114, then Period=Post-study.

The listing of all AEs will also include the AE duration (derived in days, hh:mm for AEs with onset and stop times recorded and derived in days for all other AEs with only onset and stop dates recorded), days since start of UCB6114 infusion (time if an onset time is recorded, days otherwise), seriousness and reason for seriousness, CTCAE severity grade, intensity (where a CTCAE severity grade is not recorded), pattern of event, relationship to UCB6114 and TFD/TPI and action taken with UCB6114 and TFD/TPI (including other action taken), the outcome of the AE, whether an autopsy was performed and cause of death. In addition, the listing will flag AEs that led to discontinuation from the study, TEAEs, AESIs, SAEs, UCB6114 infusion-related reactions, and DLTs. Whether an AE is related to a concomitant medication, (and separately whether it is related to the COVID-19 vaccination), the names of any co-suspect medications will also be listed.

Separate listings of all SAEs, TEAEs leading to discontinuation of UCB6114 and TFD/TPI, TEAEs leading to discontinuation of TFD/TPI only and TEAEs leading to discontinuation of the study will also be presented.

All deaths that occur on study (defined as during study treatment or within 30 days of the last dose of UCB6114) will be listed separately. This listing will include the primary cause of death and the number of days between the date of the last dose of UCB6114 and death, defined as

$$\text{Days since last dose} = (\text{Date of death} - \text{Date of latest dose of UCB6114})$$

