3.2 General study level definitions

3.2.1 First and last dose of study treatment

For each participant the start of study treatment is defined as the date and time of the first dose of UCB6114. This will be considered as the starting point of the combination therapy.

Note that TFD/TPI is taken by the participant at home prior to attending the clinic for the infusion of UCB6114 on C1D1.

Similarly, for each participant, the last dose of study treatment will be the date of the last dose of UCB6114.

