3.2.3 Study periods

Part B of the study will consist of the following study periods:

- Screening Period – up to 28 days;
- Treatment Period – Successive 28-day cycles of study treatment (UCB6114 will be administered as an iv Q2W dose on Day 1 and Day 15 of each cycle and TFD/TPI will be

administered [bid] within 1 hour of completion of morning and evening meals at home on Days 1 to 5 and Days 8 to 12, continuing until disease progression, unmanageable toxicity, or participant withdrawal). Within the first cycle of the Treatment Period, a 28-day DLT Observation Period is defined to determine safety events for dose escalation decisions using mTPI;

- Safety Follow-up Period – up to 30 days after the last dose of UCB6114.

There will be a further extended follow-up period, up to 3 months after the last dose of UCB6114, at which time the Final Visit will be performed.

For each participant, the end of the Treatment Period is defined by the date of their last dose of UCB6114.

The end of Part B of the study is defined by the date of the Final Visit for the last participant (3 months after the last participant's last dose of UCB6114), or the date of the SFU visit, if they discontinue prior to attending the Final Visit, or their last contact date if they discontinue early from the study without attending the SFU visit.

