$$\text{Total Duration of Exposure} = (\text{Date of Last Dose} - \text{Date of First Dose}) + 30$$

Note that 30 days is added to this calculation to account for a participant's continued exposure to UCB6114 and the components of mFOLFOX6 following their last dose of study treatment.

Note that a participant is deemed to have completed a full cycle of UCB6114 if they receive the planned dose of UCB6114 on Day 1 and Day 15 of each cycle and a decision was not made to discontinue UCB6114 up to and including Day 28 relative to Day 1 of a cycle.

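### Part B closes the treatment-emergent window 30 days after the last UCB6114 dose, so when that dose is a Day 1 dose, late events after TFD/TPI are missing from the TEAE tables

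*SAP*

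**What the plan says.** All sections are in the Part B plan unless Part C is named.

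- **Objective and endpoint.** Section 2.1.1 makes the safety of UCB6114 given with TFD/TPI the primary objective. Section 2.2.1.1 makes the incidence and severity of TEAEs a primary endpoint.
- **Treatment end.** Section 3.2.1: "for each participant, the last dose of study treatment will be the date of the last dose of UCB6114".
- **TEAE window.** Section 8.2: a TEAE is "any AE with a start date on or after the first dose of UCB6114 up until the last dose of UCB6114 + 30 days". Of later events it says: "These AEs will be considered as post-study AEs and will be listed only". Period of onset and the on-study death listing use the same UCB6114 limit.
- **Schedules.** Section 3.2.3: "UCB6114 will be administered as an iv Q2W dose on Day 1 and Day 15 of each cycle". TFD/TPI is taken on Days 1 to 5 and 8 to 12. Section 7 accepts a run into Day 13 when the first intake is delayed to the afternoon.
- **Exposure.** Section 8.1.2 presents summary statistics "for the total duration of exposure to TFD/TPI", computed with 30 days added to the interval between first and last TFD/TPI dose.
- **Tables.** Section 8.2 tabulates TEAEs related to UCB6114 only, and TEAEs related to UCB6114 and/or TFD/TPI.
- **Start of treatment.** Section 3.2.1: "Note that TFD/TPI is taken by the participant at home prior to attending the clinic for the infusion of UCB6114 on C1D1". For the AE listing, Section 8.2 assigns an event to Screening if it has an "onset date and time prior to the start time of UCB6114 infusion on Day 1 of Cycle 1 then Period=Screening".
- **Part C.** Section 8.1 of the Part C plan adds 30 days to exposure to account for "continued exposure to UCB6114 and the components of mFOLFOX6 following their last dose of study treatment". Its TEAE window also follows UCB6114 alone.

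**The concern.** The question is the tolerability of two treatments given together, but the window that decides which events are tabulated follows only one of them. The two do not end together when the last infusion is a Day 1 dose, because the planned TFD/TPI days of that cycle run on for up to 11 or 12 days.

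The plan is also out of step with itself. It counts 30 days beyond the last TFD/TPI dose as TFD/TPI exposure and produces tables of TFD/TPI-related TEAEs. Yet some events on those counted exposure days cannot enter the tables. The error can go one way only: late events after the backbone treatment are undercounted in a primary endpoint.

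There is a smaller mismatch at the start. An event on Cycle 1 Day 1 after the home TFD/TPI intake but before the infusion is a TEAE under the date rule and belongs to Screening under the date-and-time rule.

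**Working it through.** The plan states no figure to reproduce, so the check is day-counting on its own schedule. Days are counted from Day 1 of the participant's last cycle.

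**Inputs.** Last UCB6114 day U = 1 or 15 (Section 3.2.3). Last TFD/TPI day T = 12 on the regular schedule (Section 8.1.2), 13 under the Section 7 allowance, or 5 if only the first block is taken. TEAE allowance = 30 days (Section 8.2).

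**Formulas.** Window closes on day U + 30. The same allowance counted from TFD/TPI ends on day T + 30. Days not covered = T − U when positive, otherwise 0. Days covered after the last TFD/TPI dose = 30 − days not covered.

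| Last UCB6114 (U) | Last TFD/TPI (T) | U + 30 | T + 30 | Days not covered | Of 30 days after TFD/TPI, covered |
|---|---|---|---|---|---|
| 1 | 12 | 31 | 42 | 11 | 19 |
| 1 | 13 | 31 | 43 | 12 | 18 |
| 1 | 5 | 31 | 35 | 4 | 26 |
| 15 | 12 | 45 | 42 | 0 | 30 |
| 15 | 13 | 45 | 43 | 0 | 30 |

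The uncovered part is therefore 11/30 = 37% or 12/30 = 40% of a 30-day follow-up after TFD/TPI, when the last infusion is on Day 1 and TFD/TPI is completed. It is 4/30 = 13% if TFD/TPI stops on Day 5.

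**What happens to an event on Days 32 to 42 (or 43).** It is not a TEAE, it is labelled post-study, and it appears only in listings. If it is fatal, it still counts in the overview row for AEs leading to death, which stands apart from the row for TEAEs leading to death. It is absent from the fatal-TEAE tables, and the death falls outside the on-study death listing.

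**Effect of one missed participant.** With 3 to 9 participants per dose level (Section 2.4), one participant is 1/9 = 11 to 1/3 = 33 percentage points of an incidence. This applies only if that participant has no event of the same preferred term inside the window, since each participant counts once per term. It shows what one miss does and does not estimate how many occur.

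**Dose decisions.** The DLT period ends on Day 28, before the earliest possible window closure on Day 31. DLT counts are unaffected.

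**Part C.** The 5-fluorouracil infusion lasts 46 hours from the dosing day, so when both components stop at the same administration the gap is about 1 to 2 days.

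**The case against.** The best defence is that the anchor is deliberate. Section 3.2.1 declares the first UCB6114 dose to be the start of the combination, and the endpoint, study periods, TEAE rule and death listing all follow it. UCB6114 is the investigational product, the added 30 days in Section 8.1.2 belong to a descriptive exposure formula rather than an AE window, and late events remain in the listings. This stands as far as it goes: the rule is consistent, no data disappear from the report, and the UCB6114-anchored count is worth keeping. It does not explain why tables headed by relationship to UCB6114 and/or TFD/TPI should follow TFD/TPI for as few as 18 days.

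A reader might infer more than the document supports:

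- *That about half of participants are affected.* The SAP gives no basis for this. Planned treatment is two cycles, so the natural last infusion is Cycle 2 Day 15. Scans are targeted at Day 57 ± 7 days, and 2 × 28 + 1 = Day 57 is Cycle 3 Day 1. Progression found before that infusion also leaves a Day 15 dose as the last.
- *That participants stopping for toxicity are the ones lost.* Toxicity that stops treatment before Day 15 starts inside the window and is counted. If TFD/TPI stops with it, the gap shrinks. Only later new onsets are missed.
- *That TFD/TPI may continue alone, widening the gap.* The TEAE summaries cover discontinuation of both treatments or of TFD/TPI only. No category for stopping UCB6114 alone suggests this course.
- *That early events are lost too.* The TEAE rule uses the date, so a same-day event before the infusion enters the tables. Only its period label in the listing differs.

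**Conclusion.** The point holds for a defined group: Part B participants whose last UCB6114 dose is a Day 1 dose and who take TFD/TPI after it. For them up to 11 days of follow-up after TFD/TPI, or 12 if dosing reaches Day 13, lie outside the TEAE tables. These figures assume that TFD/TPI is completed in that cycle and that 30 days is the right allowance for both treatments, as the exposure formulas suggest. Participants whose last infusion is on Day 15 lose nothing.

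The size of any resulting bias cannot be given, because neither the share of such participants nor the rate of new events on those days can be derived from the SAP. It would not be right to conclude that deaths vanish from the summaries or that dose escalation is compromised. The Cycle 1 Day 1 mismatch is a labelling matter only. The Part C gap is small.

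**What to change.** 1. In Section 8.2 (Part B), tabulate TEAEs with onset up to 30 days after the last dose of UCB6114 or TFD/TPI, whichever is later.
2. Apply the same end limit to Period of onset and to the definition of on-study deaths.
3. Keep the UCB6114-anchored TEAE count alongside, for continuity with the protocol endpoint, and record the change in Section 3.9.
4. Reconcile the Cycle 1 Day 1 rules, so that an event before the infusion on that date is not a TEAE by one rule and a Screening event by the other.
5. Use matching wording for the mFOLFOX6 components in the Part C plan.

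The cost is wording and a derivation change. First and last dose dates of both treatments are already listed (Section 5.1), and AEs are recorded until completion or early discontinuation of Part B, so no new data collection is needed for participants still in the study on those days. TEAE counts may rise slightly.

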- Incidence of TEAEs leading to a temporary interruption of oxaliplatin infusion and/or dose reduction (overall and by tumor type);
- Incidence of TEAEs leading to a temporary interruption of leucovorin infusion and/or dose reduction (overall and by tumor type);
- Incidence of TEAEs leading to a temporary interruption of 5-fluorouracil bolus or infusion and/or dose reduction (overall and by tumor type);
- Incidence of TEAEs leading to discontinuation of UCB6114 and mFOLFOX6 (overall and by tumor type);
- Incidence of TEAEs leading to discontinuation of mFOLFOX6 only (overall and by tumor type);
- Incidence of TEAEs leading to discontinuation of oxaliplatin (overall and by tumor type);
- Incidence of TEAEs leading to discontinuation of leucovorin (overall and by tumor type);
- Incidence of TEAEs leading to discontinuation of 5-fluorouracil (overall and by tumor type);
- Incidence of TEAEs leading to discontinuation of study (overall and by tumor type);
- Incidence of DLTs (separately for during the 28-day DLT Observation Period and after the 28-day DLT Observation Period) (overall and by tumor type);
- Incidence of adverse events of special interest (AESIs) (Hy's Law – see [Section 8.2.1](#) below) (overall and by tumor type);
- Incidence of UCB6114 infusion-related reactions (defined as any TEAE with a PT from both a narrow and broad scope search of category A terms of the 'Hypersensitivity' Standardized MedDRA® Query (SMQ) – see [Section 8.2.2](#)) (overall and by tumor type);
- Incidence of TEAEs by maximum CTCAE severity grade (overall and by tumor type);
- Incidence of TEAEs related to UCB6114 only by maximum CTCAE severity grade (overall and by tumor type);
- Incidence of TEAEs related to UCB6114 and/or mFOLFOX6 by maximum CTCAE severity grade (overall and by tumor type);
- Incidence of TEAEs by maximum relationship to UCB6114 only (overall and by tumor type);
- Incidence of TEAEs by maximum relationship to UCB6114 and/or mFOLFOX6 (overall and by tumor type);
- Incidence of TEAEs by relationship to UCB6114 only;
- Incidence of TEAEs by relationship to UCB6114 and/or mFOLFOX6;
- Incidence of serious TEAEs by relationship to UCB6114 only;
- Incidence of serious TEAEs by relationship to UCB6114 and/or mFOLFOX6;
- Incidence of non-serious TEAEs by relationship to UCB6114 only;

- Incidence of non-serious TEAEs by relationship to UCB6114 and/or mFOLFOX6;
- Incidence of fatal TEAEs by relationship to UCB6114 only;

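### Section 8.2 of both SAPs has no TEAE treatment-discontinuation category for UCB6114 in its own right; read literally, an event that stops UCB6114 alone is in no such table or dedicated listing

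*SAP*

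**What the plan says.** Section 8.2 (Adverse events) of the Part B SAP handles TEAE-driven treatment discontinuation in three places.

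- Overview: "discontinuations from study treatment (UCB6114 and TFD/TPI and TFD/TPI only) due to TEAE(s").
- Tables by SOC, HLT and PT: "Incidence of TEAEs leading to discontinuation of UCB6114 and TFD/TPI (overall and by tumor type") and "Incidence of TEAEs leading to discontinuation of TFD/TPI only (overall and by tumor type"). A further table concerns leaving the study: "Incidence of TEAEs leading to discontinuation of study (overall and by tumor type").
- Listings: "Separate listings of all SAEs, TEAEs leading to discontinuation of UCB6114 and TFD/TPI, TEAEs leading to discontinuation of TFD/TPI only", followed by one for study discontinuation.

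Section 8.2 of the Part C SAP is built the same way, with "Incidence of TEAEs leading to discontinuation of UCB6114 and mFOLFOX6 (overall and by tumor type") and "Incidence of TEAEs leading to discontinuation of mFOLFOX6 only (overall and by tumor type"). It adds separate outputs for oxaliplatin, leucovorin and 5-fluorouracil.

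Elsewhere the SAPs do look at UCB6114 separately. Section 8.2 has a UCB6114 table for temporary interruption and dose reduction. Section 5.1 lists treatment discontinuation separately for UCB6114 and SoC, with the primary reason. The AE listing in Section 8.2 shows the action taken with UCB6114 and with SoC for every event.

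**The concern.** The primary objective in both parts (Section 2.1.1) is the safety profile of UCB6114 in combination. A reader of the Section 8.2 overview would expect to find how many participants at each dose level stopped UCB6114 because of a TEAE. The stated categories do not give that count unless every event that stops UCB6114 also stops SoC.

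The SoC-only category implies that this condition can fail. It has content only if some participants continue UCB6114 after SoC has stopped. If a later TEAE then stops UCB6114, that event did not stop both drugs, because SoC had already ended, and it did not stop SoC alone. Two programmers could reasonably code it differently, and on the literal wording it drops out of the discontinuation outputs.

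At stake is a descriptive safety summary that feeds the overall safety picture. No formal test or dose-finding calculation depends on it.

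**Working it through.** The plan gives no figure to reproduce, so the check maps each possible pattern of TEAE-driven stopping to the outputs of Section 8.2. SoC means TFD/TPI in Part B and mFOLFOX6 in Part C.

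| Pattern | Section 8.2 treatment-discontinuation outputs that count it |
|---|---|
| A. One event stops UCB6114 and SoC | Both-drugs row, table and listing |
| B. The event stops SoC; UCB6114 continues | SoC-only row, table and listing (Part C: also the component outputs) |
| C. SoC has already ended; a later event stops UCB6114 | None on the literal wording |
| D. The event stops UCB6114; SoC continues | None |

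Pattern C needs no assumption about the protocol beyond what the SoC-only category already implies, namely that pattern B occurs. Pattern D needs a protocol rule that the SAP does not state. The extra Part C outputs do not help with C or D, since each is defined by a component of mFOLFOX6.

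Next, where an event of pattern C or D would still be seen:

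- **General TEAE tables** (all, serious or non-serious, by grade, by relationship; Section 8.2): the event is counted, but nothing marks it as the one that stopped UCB6114.
- **Disposition table** (Section 5.1): counted by treatment group if the AE is the primary reason for stopping treatment, but without event term, SOC or PT.
- **Study-discontinuation table** (Section 8.2): only if the participant also leaves the study for the event. Section 5.1 expects some participants to remain in the study after stopping treatment.
- **UCB6114 discontinuation listing** (Section 5.1): shown for the individual, with primary reason.
- **AE listing** (Section 8.2): shown through the action taken with UCB6114.

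So the information is collected and listed, but no Section 8.2 row or table reliably gives the incidence, by dose level, of TEAEs that stopped UCB6114.

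Size of one omitted case: Section 2.4 expects 3 to 9 participants per dose level. One participant counted or not counted changes an incidence by 1/n:

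- n = 9: 1/9 = 11.1 percentage points
- n = 3: 1/3 = 33.3 percentage points

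This is only the granularity of the table. The documents do not say how often patterns C or D will occur.

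**The case against.** The strongest defence is that the scheme is deliberate. Section 3.2.1 sets the last dose of study treatment at the last UCB6114 dose, and Section 3.2.3 ends the Treatment Period there. This suggests that stopping UCB6114 ends the combination, in which case pattern D would be empty. The protocol rule is not shown, so this may be right, and pattern D can be raised only conditionally. It does not dispose of pattern C, where SoC ended first.

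For pattern C, the both-drugs category could be read as covering the event after which a participant is off both drugs. That reading is possible. The SAP gives no derivation that selects it, so the classification at least has to be written down.

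Separate tables for interruption and joint ones for discontinuation are also not a contradiction in themselves. A temporary hold can apply to one drug while permanent stopping follows a linked rule.

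A reader might go further and infer that such an event falls in no table at all, or that UCB6114 intolerance is under-reported. The documents support neither. The event stays in the general TEAE tables, can appear in the disposition table, and can be identified from two listings; no count of missed cases is available. Nor are the primary endpoints touched: Section 2.2.1.1 defines them as the incidence and severity of TEAEs and the incidence of DLTs. Dose decisions rest with the SMC on cumulative safety data (Section 4.5) and the DLT Evaluable Set (Section 3.5.7), and the recommended Phase 2 dose rests on all the information together (Section 2.3). The wording of a report table does not drive them.

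**Conclusion.** The gap in the stated categories is real and is the same in both parts. No Section 8.2 treatment-discontinuation row, table or dedicated listing is defined by the stopping of UCB6114, so a TEAE that stops UCB6114 after SoC has ended meets no category on the literal wording. The same holds while SoC continues, if the protocol allows that.

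The consequence is a risk of understating the tabulated incidence of TEAEs that stop the investigational drug. It depends on such cases occurring and on the literal reading being programmed. Each omitted case would matter at these group sizes (11 to 33 percentage points at 9 to 3 participants). The individual events remain traceable, and the primary endpoints are unaffected. It is worth correcting because the missing count concerns the drug under study and the data for it already exist.

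**What to change.** In Section 8.2 of both SAPs, in the overview, the SOC/HLT/PT tables and the dedicated listings:

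1. Add a category for TEAEs leading to discontinuation of UCB6114, with or without discontinuation of SoC, derived from the action taken with UCB6114 recorded for each AE.
2. Keep the SoC-only outputs and, in Part C, the component outputs.
3. State how an event that stops UCB6114 after SoC has already ended is classified.

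A sentence saying that SoC may not continue after UCB6114 stops would settle only pattern D; item 3 is still needed for pattern C.

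The cost is one extra row, one table and one listing per part, plus a sentence of definition. No new data are needed, since action taken is already listed by drug. The change concerns reporting only and sets no rule for when either drug should be stopped.
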